11.3.2 Analysis Plan

We will calculate point estimates and 95% confidence intervals for:

1. Percentage of patients who had true lesions.
2. Sensitivity and specificity of ^{68}Ga -PSMA-11 PET/CT.

11.4 Sample Size

We expect to recruit 200 patients over the course of this trial. The number of lesions cannot be predicted at this time, however, if our expectation of a 30% discovery rate is correct, the resulting confidence interval would be roughly ± 7 percentage points, and confidence intervals for specificity/sensitivity would be roughly ± 10 percentage points.

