INVESTIGATIONAL PRODUCT	⁶⁸ Ga-PSMA-11; also known as: 
 • DFKZ-11 • HBED-CC PSMA • The “Heidelberg compound”
PRIMARY OBJECTIVE	To evaluate ⁶⁸ Ga-PSMA-11 PET/CT for detection of recurrent prostate cancer after initial therapy in patients with elevated PSA
SAMPLE SIZE	200 participants
GOALS	
Prospective single-center, single-arm study.
 
HYPOTHESES
 
 1. At least 30% of these patients will have one or more lesions detected on ⁶⁸Ga-PSMA-11 PET/CT. 2. ⁶⁸Ga-PSMA-11 PET/CT will have sensitivity and specificity of at least 70% in this context. 
STATISTICAL TEST
 
We will calculate point estimates and 95% confidence intervals for:
 
 1. Percentage of patients who had true lesions. 2. Sensitivity and specificity of ⁶⁸Ga-PSMA-11 PET/CT. 
STATISTICAL POWER AND SAMPLE SIZE
 
We expect to recruit 200 patients over the course of this trial. The number of lesions cannot be predicted at this time, however, if our expectation of a 30% discovery rate is correct, the resulting confidence interval would be roughly +/- 7 percentage points, and confidence intervals for specificity/sensitivity would be roughly +/- 10 percentage points.

SCHEMA

Eligible participant with prostate cancer

LIST OF ABBREVIATIONS AND DEFINITION OF TERMS

Ga-68; ^{68}Ga	Gallium-68
IRB	Institutional Review Board
IV	Intravenous
MRI	Magnetic resonance imaging
NPV	Negative predictive value
PPV	Positive predictive value
PET	Positron emission tomography
SUV	Standardized Uptake Value
PSMA	Prostate Specific Membrane Antigen

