10.1.1 Primary Outcome

Primary Outcome Title: Confirmation of Prostate Cancer Recurrence

Description: Prostate cancer patients with suspected prostate cancer recurrence will be evaluated with ^{68}Ga -PSMA-11 PET/CT and conventional imaging. The outcome will be reported as the percentage of participants for whom tumor lesions are identified by ^{68}Ga -PSMA-11 PET/CT, and for whom tumor lesions are identified by histopathology/biopsy and/or conventional imaging follow-up. The outcome is reported as percentages without dispersion.

Time Frame: 1 year

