10.2 Measurement Methods

Visually PET positive lymph nodes will be considered greater than blood pool (adjacent or mediastinal blood pool); PET positive bone lesions will be considered greater than physiologic bone marrow; PET positive prostate, prostate bed and visceral lesions will be considered greater than physiologic background activity of the involvement organ or anatomic site.

Sites of suspected metastatic disease will be graded as positive or negative on two separate analysis, for a more sensitive or specific visual read respectively.

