11.3 Key variables

11.3.1 Analysis Population

All lesions identified by ⁶⁸Ga-PSMA-11 PET/CT.

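### Hypothesis 1 puts its 30% target on PET-detected lesions while the plan analyses true lesions, and the population and single ±10 for sensitivity and specificity lack per-patient denominators

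*Combined protocol and SAP*

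**What the plan says.** The synopsis states two hypotheses. The first is "At least 30% of these patients will have one or more lesions detected on" ⁶⁸Ga-PSMA-11 PET/CT; it does not mention confirmation. The second is that the scan "will have sensitivity and specificity of at least 70% in this context".

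The first quantity to be estimated, in the synopsis and again in 11.3.2, is "Percentage of patients who had true lesions". Section 11.4 uses a third term: "if our expectation of a 30% discovery rate is correct, the resulting confidence interval would be roughly" ±7 percentage points. It adds that "confidence intervals for specificity/sensitivity would be roughly" ±10 points, one figure for both measures, and says that the number of lesions cannot be predicted.

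Section 10.1.1 reports men with lesions identified by PET/CT and men "for whom tumor lesions are identified by histopathology/biopsy and/or conventional imaging follow-up". This can be read as one joint percentage or as two. The analysis population in 11.3.1 is "All lesions identified by" the study scan. Section 10.1.2 promises sensitivity and specificity by participant.

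On what counts as PET-positive, 10.2 says "Sites of suspected metastatic disease will be graded as positive or negative on two separate analysis", one more sensitive and one more specific. Section 5.3 has three readers and no rule for combining them.

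**The concern.** The 30% target is attached to three differently worded quantities, and only one of them clearly excludes false positives. The 30% is also exactly the false-positive rate that a scan at 70% specificity would produce. A report could therefore say that Hypothesis 1 was met without this showing that the scan finds recurrence. Because the wording is open, the choice between detected and confirmed could be made after the data are seen.

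The accuracy estimates have a separate problem. Sensitivity is estimated in men with disease and specificity in men without it, so their precision depends on how many men fall in each group and how many have a reference result. The plan gives neither number, and its stated population leaves out PET-negative men.

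**Working it through.** **Inputs.** From the plan: 200 men (11.4), the 30% and 70%/70% values (synopsis), and 95% intervals (11.3.2), taken as two-sided. The plan gives no prevalence of reference-positive disease (π) and no number verified. Both are assumptions here and are varied.

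**1. The plan's ±7.** 1.96 × √(0.30 × 0.70 / 200) = 6.35 points; the exact interval for 60/200 is 23.7% to 36.9%. Roughly ±7 reproduces as a rounded-up figure.

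**2. Detected versus confirmed.** PET-positive rate = Se·π + (1 − Sp)(1 − π). At Se = Sp = 0.70 this is 0.70π + 0.30(1 − π) = 0.30 + 0.40π. The rate of men who are PET-positive and confirmed, with all men verified, is 0.70π. The last two columns give the binomial chance of at least 60/200.

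| Assumed π | PET-positive | False share of PET-positives | Confirmed | Chance, detected | Chance, confirmed |
|---|---|---|---|---|---|
| 20% | 38% | 0.24/0.38 = 63% | 14% | 99.3% | <0.1% |
| 30% | 42% | 0.21/0.42 = 50% | 21% | >99.9% | 0.2% |
| 42.9% | 47% | 0.171/0.471 = 36% | 30% | >99.9% | 53% |
| 50% | 50% | 0.15/0.50 = 30% | 35% | >99.9% | 94% |
| 80% | 62% | 0.06/0.62 = 10% | 56% | >99.9% | >99.9% |

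Away from the floor the result changes. With Se = 0.70 and Sp = 0.90, the PET-positive rate is 0.10 + 0.60π. It reaches 30% at π = 33%, where the false share is 0.0667/0.30 = 22%.

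**3. Analysis population.** A set made up only of PET-identified lesions has no false negatives and no true negatives. Sensitivity, TP/(TP + FN), would be 100% by construction. Specificity, TN/(TN + FP), would have a numerator of zero. PPV could still be calculated.

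**4. The ±10.** At 70%, n = 1.96² × 0.70 × 0.30 / 0.10² = 80.7, so 81 men are needed in each group. With all 200 verified, both half-widths are within 10 only if 81 to 119 men are reference-positive, that is 40.5% to 59.5%. Half-widths in points (sensitivity / specificity, both at 70%), with n = verified × π and verified × (1 − π):

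| Verified | π = 30% | π = 50% | π = 80% |
|---|---|---|---|
| 200 | 11.6 / 7.6 | 9.0 / 9.0 | 7.1 / 14.2 |
| 150 | 13.4 / 8.8 | 10.4 / 10.4 | 8.2 / 16.4 |
| 100 | 16.4 / 10.7 | 12.7 / 12.7 | 10.0 / 20.1 |

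More lenient readings widen the window. If both measures are 80%, 62 men per group suffice (31% to 69%, all verified). If roughly ±10 may stretch to 12 points at 70%, 57 per group suffice (28.5% to 71.5%).

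**The case against.** The best defence is that Hypothesis 1 is about yield and Hypothesis 2 about accuracy, so the first need not prove the second. PPV is in the primary endpoint (10.3), and PPV, NPV and specificity are secondary (10.1.2, 10.4). The analysed item already says true lesions, and the title of 10.1.1 speaks of confirmation. No formal test or decision rests on Hypothesis 1. All of this stands. It limits the harm to what Hypothesis 1 can conclude, but it does not give the 30% a single meaning.

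A reader might infer that Hypothesis 1 is empty at any performance, or that the trial could succeed in men without disease. The documents do not support this. The 70% values are minimums, and with higher specificity the detected target does depend on prevalence. Zero prevalence is only a limiting case: 3.1 requires biochemical recurrence, so the low-prevalence rows should not be taken as the expected ones. Reference-positive prevalence may nevertheless be lower than true recurrence. It rests on biopsy or conventional imaging within a year, and 10.1 expects conventional imaging to give false negatives.

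A reader might also infer that ±10 is an arithmetic error or that 200 men are too few. Neither is shown. The plan says roughly and admits that the number of lesions is unknown, and at 30% prevalence with all men verified the two half-widths (11.6 and 7.6) lie on either side of 10.

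**Conclusion.** The point holds as a mismatch of definitions and a gap in stated inputs. Neither ±7 nor ±10 is shown to be wrong.

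- **Hypothesis 1.** Detected and confirmed are different targets. At the 70%/70% floor with all men verified, the chance of reaching 60/200 at 30% prevalence is above 99.9% for one and 0.2% for the other; by 80% prevalence both are near certain. The false share at the floor falls from 63% to 10% between 20% and 80% prevalence.
- **Population.** Read literally, 11.3.1 cannot deliver the sensitivity and specificity promised in 10.1.2 and 11.3.2. This needs no assumption about prevalence.
- **Precision.** One ±10 for both measures at 70% needs a near-even split of reference-positive and reference-negative men and at least 162 verified. Outside 40.5% to 59.5% prevalence, one of the two exceeds 10 even with all 200 verified.

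All prevalences and verified numbers are assumptions, since the plan gives none. The point is worth fixing because wording alone settles it and the wording determines what can be claimed.

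**What to change.** 1. **11.3.1:** define per-patient populations. Use all scanned men for detection, and all men with a reference result, PET-positive or PET-negative, for sensitivity and specificity.
2. **Synopsis, 10.1.1, 11.3.2 and 11.4:** state the 30% on one quantity, men who are PET-positive and confirmed. Alternatively, keep detection as a yield measure explicitly paired with PPV. Under either option:
   - Reconcile the reference standard: 10.3 uses histopathology/biopsy, while 10.1.1 and 10.4 bring in conventional imaging follow-up.
   - Name which read in 10.2, and what combination of the three readers, defines PET-positive.
   - Report the raw PET-positive rate and the number of unverified PET-positive men beside the result.
3. **11.4 and synopsis:** replace the single ±10 with separate sensitivity and specificity half-widths over a range of assumed prevalence and number verified, as in the second table above.

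**Cost.** The changes are wording and one short table, with no extra men, scans or follow-up; N is unchanged. A confirmed 30% target is appreciably stricter. At 70% sensitivity with all men verified, the chance of at least 60/200 is about 53% at 42.9% prevalence and 94% at 50%. It also depends on complete follow-up, because unverified PET-positive men count against it. If an assumed 75% are verified, regardless of disease and PET result, an expected 30% needs 0.30/(0.70 × 0.75) = 57% prevalence instead of 43%. Pairing detection with PPV avoids moving the target. The stated precision will look less favourable for one of the two measures at most prevalences.

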11.5 Accrual estimates

We expect the accrual of 40 patients each year for 5 years.

Inclusion/Exclusion Criteria Checklist

Protocol Title:	68Ga PSMA-11 PET/CT for detection of recurrent prostate cancer after initial therapy in patients with elevated PSA and non-contributory bone scintigraphy, computed tomography (CT) or magnetic resonance imaging (MRI)		
Protocol Number:	IRB-35932 / PROS0076		
Principal Investigator:	[name], MD		

Inclusion Criteria – Yes must be checked to be eligible (From IRB-approved protocol)		Yes	No	Supporting Documentation
1. ≥ 18 year-old				
2. Histologically-proven prostate adenocarcinoma				
3. Rising PSA after definitive therapy with prostatectomy or radiation therapy (external beam or brachytherapy)				
a. Post radical prostatectomy (RP) – AUA recommendation				
i. PSA greater than 0.2 ng/mL measured after at least 6 weeks from radical prostatectomy				
ii. Confirmatory persistent PSA greater than 0.2 ng/mL (total of two PSA measurements greater than 0.2 ng/mL)				
b. Post-radiation therapy –ASTRO-Phoenix consensus definition				
i. A rise of PSA measurement of 2 or more ng/mL over the nadir				
4. Able to provide written consent				
5. Karnofsky performance status of ≥ 50 (or ECOG/WHO equivalent)				

Exclusion Criteria – No must be checked to be eligible (From IRB approved protocol)		Yes	No	Supporting Documentation
1. Investigational therapy for prostate cancer				
2. Unable to lie flat, still or tolerate the study scan				
3. Prior history of any other malignancy within the last 2 years, other than skin basal cell or cutaneous superficial squamous cell carcinoma that has not metastasized and superficial bladder cancer.				

*All subject files must include supporting documentation to confirm subject eligibility. The method of confirmation can include, but is not limited to, laboratory test results, radiology test results, subject self-report, and medical record review.

Statement of Eligibility

